**Enrollment feasibility.** The two FQHCs provide primary care to over 100,000 unique patients a year, who are cared for by 50 providers. Each provider sees approximately 2,000 asthma patients. Using a conservative estimate of 8% asthma prevalence, 160 unique patients with asthma are served per provider. Based on our preliminary studies we expect ~69% of subjects screened will have uncontrolled asthma (n=110 patients / PCP); of these, 97% will screen positive on the CAM-A yielding 107 eligible patients / PCP. Thus, we have an adequate patient pool from which to draw 10 patient subjects / PCP.

**Blinding.** Patient codes, tied to PCP assignment (active vs. control), will be entered into a tablet prior to the completion of the CAM-A by the RA. The meaning of these codes will not be known to the RA. Using these codes, the software will trigger the tablet to load either the **BREATHE** intervention steps or the attention control timer (described below) after the CAM-A has been completed. These screens will be hidden from the patient and the RA by two “hold” screens warning the RA/patient subject not to advance further. We will assess the adequacy of blinding of the subject and the RA as a process outcome at the end of the study. Both active and control PCPs will receive the tablet from the RA and the results of the lung function testing (FEV1). The RA will set up two digital recorders to capture the audio of the office visit and then leave the room. The RA will be instructed to stay close by to monitor the end of visit but not close enough to overhear the conversation. The statistician ([name]) will be blinded. The PI, Project Manager and database manager will not be blinded.

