### **Survey Administration.**

The PI and/or Project manager (unblinded) will administer the following surveys after the clinician has signed informed consent: Demographic and professional history; PCMI.

The RA (blinded) will be responsible for all patient data collection.

Surveys, Diaries, Testing, Interviews and Fidelity Checks	Type of Data; how collected	Who will collect	Data source	Pre - visit 1 (V1 )	Visit 1 Baseline	Within 24 hours of V1	Visit 2 ~ 4 weeks after V1	Visit 3 ~ 4 weeks after V2	Visit 4 ~ 4 weeks after V1	Post-trial
Asthma Control Questionnaire – 6 items (ACQ6) without item 7 (FEV1)	Survey; Collected by phone	RA or PM	Patient	X						
Demographics	Survey; Collected by phone	RA or PM	Patient	X						
Conventional and Alternative Management for Asthma (CAM-A)	Survey; Collected on tablet	RA	Patient	X					X	
Asthma history	Survey; Paper and pencil	RA	Patient		X					
Forced Expiratory Volume in One Second (FEV1) alone – item & on the ACQ	Non-invasive measure of airflow obstruction; hand-held spirometer	RA	Patient; hand-held spirometer		X					
Newest Vita Sign (NVS)	Survey; Paper and pencil survey	RA	Patient		X					
Shared Decision Making Questionnaire- 9 items (SDMQ9)	Survey; Paper and pencil	RA	Patient		X					
Medication Adherence Record Scale-Asthma (MARS-A)	Survey; Paper and pencil survey	RA	Patient		X		X	X	X	
Patient reported Outcome Measurement Information System- 29 items (PROMIS-29)	Survey; Paper and pencil survey	RA	Patient		X		X	X	X	
Asthma Quality of Life Questionnaire (AQLQ)	Survey; Paper and pencil survey	RA	Patient		X		X	X	X	
Patient Immediate post-visit debriefing and blinding assessment	Survey; Paper and pencil	RA	Patient		X					
Asthma Control Questionnaire – 7 items (ACQ7) with FEV1	Survey and non-invasive measure of airflow obstruction; Paper and pencil and hand-held spirometer	RA	Patient; hand-held spirometer				X	X	X	
Asthma daily diary	Diary; Paper and pencil	Patient	Patient		DISPENSED		X	X	X	
Doser electronic dose counter	Electronic dose counter	RA will download by hand	Patient; Doser electronic counter		DISPENSED		X	X	X	
Client Satisfaction Questionnaire 8 items (CSQ8)	Survey; Paper and pencil	RA	Patient						X	
Post-trial interviews	Interviews, Audio recorded	PI	Patients, loved ones and providers							X
Provider Data Collection Form	Survey; Paper and pencil	PM or PI	Providers	X						

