Provider Co-Management Index (PCMI)	Survey; Paper and pencil	PM or PI	Providers	X						
Readiness Ruler	Scale; Collected on tablet	Provider	Patient		X					
Provider Immediate post-visit debriefing	Survey; Paper and pencil	RA	Providers		X					
Brief Negotiated Intervention (BNI) Adherence Scale (Active condition)	Fidelity Checklist	Coder (TBD)	Audio files of patient-provider visits			X				
Fidelity Check Attention control condition	Fidelity Check	Coder (TBD)	Audio files of patient-provider visits			X				

**Intervention Condition.** PCPs randomized to **BREATHE** will receive the tablet which, when the screen is advanced by the PCP, will prompt the PCP through a 7-minute, 4-step brief intervention tailored to respond to the patient's specific beliefs endorsed on the CAM-A using content identified in our CBPR development phase (focus groups). See the Brief Negotiated Intervention (BNI) for the full intervention details.

**Step 1: Raise the subject (1½ minute).** PCP establishes rapport using persuasive communication techniques and assesses the patient's disease knowledge, perception of asthma control, quality of life (QoL), self-care preferences, and motivation for enhanced asthma control, exploring specific beliefs that may affect adherence.

**Step 2: Provide feedback (1½ minutes).** PCP provides feedback to the patient based on assessments made in the prior step. The PCP candidly discusses the patient's uncontrolled asthma and specific beliefs in the context of ICS non-adherence, drawing a connection between current symptoms and ICS non-adherence.

**Step 3. Enhance motivation (2 minutes).** The PCP attempts to enhance the patient's motivation to increase ICS adherence using motivational interviewing techniques such as collaboration, empathy, concern, and acceptance of ambivalence about self-management. In this step, the PCP may elicit the patient's beliefs regarding the benefits, and negative sequelae, of their current self-management approach (pro/con).

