## **STATISTICAL PROCEDURES**

**Patient data collection.** While we recognize the need for longer follow-up in a full-scale RCT, trained RAs, blind to treatment status, will collect data four times: baseline and 1-month, 2-month, and 3-month follow-up. To address the risk of assessment reactivity, both groups will receive an equal number of assessments.

**Patient subject measures (see Table 1).** The primary outcome measure is patient-reported asthma control over 3 months as measured with the ACQ. We will collect the ACQ and secondary outcomes including objective measures of airflow obstruction (FEV1), asthma QoL using the Asthma Quality of Life Questionnaire - AQLQ and ICS adherence using the Medication Adherence Record Scale-Asthma (MARS-A). The MARS-A correlates with objective ICS adherence as measured by electronic monitoring and ICS fill/refill claims data. Other surveys that will be used to characterize the subjects include the asthma history, Newest Vital Sign, the PROMIS-29 and the Shared Decision Making Questionnaire- 9 items. All patient subjects will

also be asked to complete the Patient Debriefing and Blinding Assessment survey immediately after V1. The blinded RA will dispense a 30-day asthma diary (4th grade reading level) to all subjects after each data collection visit. The Doser™, an electronic monitor capable of recording 30-days ICS use, will be attached to compatible ICS. Due to unique delivery systems for ICS, there is no single electronic device to monitor all ICS types. No change in ICS is required to participate in the Doser tracking log. Finally, we will collect patient satisfaction using the Client Satisfaction Questionnaire-8 (CSQ-8) at 3-months..

**CP measures.** PCPs will be asked to complete a demographic and professional history form and one survey at the time they sign informed consent: the Provider Co-Management Index (PCMI). The PCMI is a measure of PCP shared management. All PCPs will also be asked to complete the Provider Debriefing survey immediately after V1.

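### The blinded research assistant collects each PCP's post-visit debriefing form with no stated shield, an avoidable risk of unblinding

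*Combined protocol and SAP*

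**What the plan says.** On who gathers patient data, Survey Administration states: "The RA (blinded) will be responsible for all patient data collection". Statistical Procedures agrees: "trained RAs, blind to treatment status, will collect data four times", at baseline and at one, two and three months.

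On protecting the RA's blinding, the Blinding paragraph has the RA enter patient codes into the tablet: "The meaning of these codes will not be known to the RA". Hold screens conceal the arm-specific content, and the RA leaves the room for the visit and stays out of earshot. The adequacy of the RA's blinding is assessed when the study ends. The same paragraph lists the staff who know the allocation: "The PI, Project Manager and database manager will not be blinded".

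On provider surveys, the text reads: "The PI and/or Project manager (unblinded) will administer the following surveys after the clinician has signed informed consent: Demographic and professional history; PCMI". The table matches this, giving the Project Manager or PI as collector of both. The Provider Consent paragraph also reserves PCP consent for the PI or Project Manager, on the ground that they are unblinded.

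The row "Provider Immediate post-visit debriefing" differs. It is a paper survey with providers as the source, it is marked at Visit 1, and its collector is the RA. Statistical Procedures confirms the timing and that both arms are covered: "All PCPs will also be asked to complete the Provider Debriefing survey immediately after V1".

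**The concern.** A PCP cannot be blind. One group is trained and prompted through the four BREATHE steps; the other sees a seven-minute timer and talks about diet and exercise. The plan keeps the RA away from that session, then has the RA take a form from the PCP directly afterwards. A written answer or a passing remark could give away the arm.

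Randomisation is by PCP, so such a leak would not stop at one patient. It would tell the RA the arm of every patient of that PCP, including those not yet enrolled. According to section d of the DSMP, the same research assistant does both consenting and data collection. A leak could therefore touch later recruitment as well as outcome measurement.

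**Working it through.** The plan gives no figure to reproduce. The check is a comparison of the relevant provisions, followed by simple counts of how far one leak could reach.

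**Who handles each planned PCP contact**

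- PCP consent: PI or Project Manager, unblinded (Provider Consent).
- Provider data form and PCMI: PI or Project Manager, unblinded (Survey Administration, text and table).
- Tablet and lung function result handed to the PCP: RA, before the session (Blinding).
- Post-visit debriefing: RA, after the session (table).

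The debriefing is the only provider survey that the table gives to blinded staff, and the only planned handover from PCP to RA of a completed form about a session just delivered.

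**When each safeguard acts**

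- Codes and hold screens: before the session.
- RA out of the room and out of earshot: during the session.
- Blinding assessment: at the end of the study, so it can detect a leak but not prevent one.
- For the debriefing form: no sealed return, direct entry or handling instruction is stated.

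**Reach of one leak**

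Inputs: 8 PCPs (PCP Recruitment), 10 patients per PCP and 80 in all (Patient Participants & Consent), 3 follow-up visits (Statistical Procedures), 10% attrition at 12 weeks (Power & Sample Size).

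- Debriefings, if one follows each Visit 1: 8 × 10 = 80. The plan states no count.
- Patients whose arm one leak would reveal: up to 10, and 10 / 80 = 12.5%.
- Follow-up assessments for those patients: 10 × 3 = 30.
- Ceiling if all 8 PCPs were revealed: 30 × 8 = 240 before attrition. With 10% attrition, 72 patients complete. If the 8 dropouts miss only the last visit, 240 − 8 = 232 remain; if they miss all three, 72 × 3 = 216 remain.
- Later patients, if enrolment is sequential and the first debriefing gives the arm away: 9 of 10 for that PCP. If this happened for all 8 PCPs, 9 × 8 = 72, and 72 / 80 = 90%.

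These are counts of exposure. They are not estimates of bias.

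**Which measurements are open to influence**

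- RA-run: hand-held spirometry at Visits 2 to 4, which gives FEV1 (secondary) and item 7 of the ACQ (one of seven items in the primary measure).
- Patient-reported: the six ACQ symptom items, AQLQ and MARS-A. Here the RA's influence is limited to how the survey is administered.
- Least exposed: the patient-completed diary and the electronic dose counter, although the RA downloads the latter by hand.
- Baseline spirometry for a given patient comes before that patient's debriefing, because the PCP receives the result for the visit. It is exposed only for later patients of a PCP whose arm is already known.

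**The case against.** The strongest reply is that the mechanism is unproven. The form is a paper survey that the PCP completes; nothing makes it an interview, and nothing says the RA reads it, discusses it or enters it. Its items are not in the documents. This stands. A reader might infer that the RA will be unblinded, but the documents support only a risk.

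The second reply is that this is not the only route. The RA hands over the tablet, waits nearby for the visit to end, collects the patient's own debriefing and blinding assessment and the SDMQ9 at Visit 1, and sees the same patients three more times. This also stands, and changing the debriefing procedure will not close those routes. It does not justify keeping one that is unnecessary. The tablet handover comes before the session, and the plan intends patients to be blind, whereas the PCP certainly knows the arm.

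The third reply is that most outcomes, including the bulk of the primary one, are patient-reported. This is right, and it rules out the inference that the primary result would be seriously distorted. The documents also do not describe how the RA conducts spirometry beyond using trained staff and a calibrated device, so the degree of RA influence is unknown.

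The last reply is that this is a feasibility pilot that will itself report whether RA blinding held. That is useful learning, but an end-of-study check cannot undo a leak.

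A practical objection also stands. The PI and Project Manager give their surveys once, at PCP consent. Nothing places them at up to 80 visits across two centres, so collection in person could need extra staff time.

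**Conclusion.** The point holds as an avoidable risk to the RA's blinding that is out of line with the plan's own arrangements for other provider contacts. One leak would reveal the arm of up to 10 patients (12.5% of the sample) and up to 30 follow-up assessments. What is exposed is mainly spirometry, survey administration, and the consent and baseline testing of that PCP's later patients.

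This rests on three assumptions: one debriefing per Visit 1, sequential enrolment within a PCP (for the effect on later patients), and some chance that the form or the handover reveals the arm. The documents give no basis for putting a figure on that chance, so no size of bias in ACQ or FEV1 can be stated. The total of 240 assessments is a ceiling that requires all 8 PCPs to be revealed and nobody to drop out. It should not be read as the expected damage.

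This is a cheap improvement worth making. It is not a flaw that undermines the trial.

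**What to change.** Have each PCP complete the debriefing alone and seal it in an envelope addressed to the Project Manager. Instruct the RA not to read, discuss or enter the form. Change the collector cell in the Survey Administration table to match, for example to *PCP self-completes; returned sealed to Project Manager*, and add one sentence to the Blinding paragraph.

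The cost is envelopes and their handling, and the RA can no longer check a form for completeness on the spot. Sample size and power do not change. Collection in person by the Project Manager or PI is not required.

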## **STATISTICAL PROCEDURES**

**Patient data collection.** While we recognize the need for longer follow-up in a full-scale RCT, trained RAs, blind to treatment status, will collect data four times: baseline and 1-month, 2-month, and 3-month follow-up. To address the risk of assessment reactivity, both groups will receive an equal number of assessments.

**Patient subject measures (see Table 1).** The primary outcome measure is patient-reported asthma control over 3 months as measured with the ACQ. We will collect the ACQ and secondary outcomes including objective measures of airflow obstruction (FEV1), asthma QoL using the Asthma Quality of Life Questionnaire - AQLQ and ICS adherence using the Medication Adherence Record Scale-Asthma (MARS-A). The MARS-A correlates with objective ICS adherence as measured by electronic monitoring and ICS fill/refill claims data. Other surveys that will be used to characterize the subjects include the asthma history, Newest Vital Sign, the PROMIS-29 and the Shared Decision Making Questionnaire- 9 items. All patient subjects will

also be asked to complete the Patient Debriefing and Blinding Assessment survey immediately after V1. The blinded RA will dispense a 30-day asthma diary (4th grade reading level) to all subjects after each data collection visit. The Doser™, an electronic monitor capable of recording 30-days ICS use, will be attached to compatible ICS. Due to unique delivery systems for ICS, there is no single electronic device to monitor all ICS types. No change in ICS is required to participate in the Doser tracking log. Finally, we will collect patient satisfaction using the Client Satisfaction Questionnaire-8 (CSQ-8) at 3-months..

**CP measures.** PCPs will be asked to complete a demographic and professional history form and one survey at the time they sign informed consent: the Provider Co-Management Index (PCMI). The PCMI is a measure of PCP shared management. All PCPs will also be asked to complete the Provider Debriefing survey immediately after V1.

**Power & Sample Size.** With a sample size of 10 patients/PCP and 4 PCPs in both intervention groups (total  $n=10*4*2=80$ ), and a conservative estimate of 10% attrition at 12 weeks, we calculated the reliability of estimated mean score differences between the two groups. Power calculations were based on: (1) 4 repeated observations / patient over the 3-month follow-up with a correlation of  $\rho=0.8$  between repeated measures; (2) intra-cluster correlation among PCPs=0.2 to account for clustering of patients from the same PCP; and (3) linear mixed models to estimate mean score differences. For the ACQ, the half-width of 95% CI for the estimated mean score difference between the 2 groups is 0.32 (assuming  $SD=0.76$ ). This is equivalent to having 91% power to detect a medium effect size (Cohen's  $d=0.5$ ). We are powered to detect a clinically meaningful difference on ACQ and AQLQ.

**Qualitative analysis.** Qualitative descriptive data analysis will focus on refining the intervention (see draft of sample questions for PCPs and patient/loved ones). De-identified transcripts will be entered into NVivo 11.0 for coding and analysis. Three coders working independently of each other will systematically read the transcripts to identify emerging themes; the Patient Advocate consultant will serve as one coder. Themes will be compared between coders and disagreements will be reconciled by consensus. As we have done in the past, we will employ an iterative process in which themes in earlier interviews will be presented to subsequent interviewees to ascertain if they resonate with them; unendorsed themes will be discarded. Typically, this iterative process continues until no new essential information is obtained, an endpoint known as data saturation. Data saturation usually occurs after in-depth interviews with 20-30 individuals per category (e.g., patient, loved one, PCP). However, the focus of these more limited interviews are simply to assess acceptability and identify categorical level findings. We will use interview data to triangulate with the 8-item Client Satisfaction Questionnaire (CSQ-8) that is completed by all 80 subjects. All retained responses that are similar will be grouped together by code words to form the final thematic categories. Transcripts, field notes and codes will serve as points of triangulation.

## **DSMP**

The proposed study includes (1) a development phase where we will develop the intervention using focus groups with patients and patients' family/support persons (N = 60) with primary care provider (PCP) review, and (2) a pilot validation phase where we will conduct a pilot randomized controlled trial with 8 PCPs from Philadelphia primary care clinics randomized to one of two study arms: (1) the **BREATHE** intervention, or (2) usual care. We will follow 10 Black adult patients with uncontrolled asthma per PCP (N = 80) for three months post-intervention. Post-study refinement will include additional interviews with patients, family/support persons and PCPs who did and did not participate.

This Human Subjects Research meets the NIH definition of "Clinical Research." Institutional review board (IRB) permission for the study will be obtained from the Columbia University (IRB of record) and will be reviewed annually. Although the NIH requires data and safety monitoring for any clinical trials, having an Safety Monitoring Committee (SMC) – a small group of 3 experts who are independent of the protocol who review data from a particular study including independent investigators and biostatisticians - may be appropriate if the study includes multiple sites and a vulnerable population. Because the application includes a feasibility trial in urban minority adults from different clinical sites, and because inclusion criteria require that participants have uncontrolled asthma, we will establish an SMC.

**a. Monitoring entity or who will monitor the study.** While the behavioral intervention itself is a low risk intervention, participants must have uncontrolled asthma to be eligible for enrollment. Because of this, we will appoint an SMC to establish a threshold for asthma exacerbations (defined below) with the PI's input. The SMC will be appropriate experts who are independent of the study and available in real time to review and recommend appropriate action regarding adverse events and other safety issues.

The SMC, appointed by the PI and approved by the Program Officer include:

Although not members of the SMC, the research team has a responsibility to the SMC. These include the **Principal Investigator** (PI) who is responsible for ensuring participants' safety on a daily basis for the protocol that will be overseen by the same SMC. The SMC will act in an advisory capacity to the PI and to NINR to monitor participant safety, evaluate the progress of the study, and review procedures for maintaining the confidentiality of data and the quality of data collection, management and analyses. The PI will be responsible for timely communication of safety data to the appointed SMC, appropriate response to any safety concern identified by the SMC, and compliance with any actions that the SMC identifies as being needed. The PI will also be responsible for all reporting requirements. Lastly, the PI will train all project staff to recognize and report any adverse event immediately to her. The **project manager** and/or the data manager will review all data collected by the research assistant (RA) and communicate data and/or safety concerns in real time to the PI. The **RA** will notify the project manager and/or the PI in real-time when data collection indicates a possible data/safety concern. Details are provided in (d) below.

**b. Procedures for 1) monitoring study safety to include monitoring schedule, auditing selected cases for compliance with IRB requirements, conformance with informed consent requirements, verification of source documents, and investigator compliance; 2) minimizing research-associated risk, and 3) protecting the confidentiality of participant data.** For the pilot test, we will use the following strategies to monitor and deal with possible adverse impacts. Research participants will be told to contact research staff (who will return calls within 72 hours) at any point during the entire project if they have any questions or concerns about their participation. The PI and researchers will meet daily to review adverse or unexpected events data and weekly to review data reports generated by the data management team regarding all study-related activities. This will include case detection, consent, intervention activities, and surveys/interviews. The SMC will act in an advisory capacity to the PI and NINR to monitor participant safety, evaluate the progress of the study, and to review procedures for maintaining the confidentiality of data and the quality of data collection, management and analyses.

Recruitment. We will recruit patients using methods we have used successfully in prior studies. The federally-qualified health center (FQHC) administrator will create a potential list of subjects using a combination of ICD-10 (Asthma 493)-

specific queries of the electronic membership records and searching of scheduled patient visits for the FQHC PCPs to review. The research team will receive only the names and contact information of those the PCP permits the team to contact. We will also accept subjects who respond to posted recruitment flyers.

**Informed Consent.** The study team will read the informed consent and HIPAA to the subject and will discuss it section by section. When subjects have had all questions and concerns addressed, they will be asked to sign the consent indicating they are entering into the study voluntarily. Participants will be given a copy of the HIPAA and the signed informed consent document; a copy of the informed consent and HIPAA will be maintained with the study team.

**Auditing Selected Cases.** Fidelity to consenting, data collection and the intervention will be evaluated in the following manner. Twenty percent of all visits will be randomly selected for auditing of the informed consent and data collection protocols. In addition, intervention fidelity will be assessed by reviewing audiotapes of 20% of randomly selected visits (with the exception of the first visit; all first visits be reviewed) to be rated by three independent blinded raters. At least one additional file per PCP will be reviewed prior to enrollment of their 5th patient subject, to evaluate drift and the length of BREATHE sessions, and length, content and contamination, if any, of control sessions. Consultant [name] will conduct additional training to enhance intervention fidelity and brevity if problems are identified.

**Minimizing research –associated risk.** While the behavioral intervention itself is a low risk intervention, participants must have uncontrolled asthma to be eligible for enrollment. Because of this, we will ask the SMC to use the established threshold for asthma exacerbations (defined below) with the team's input (see details below).

The risk associated with the focus group procedures and intervention may include psychological distress due to sharing of personal information and the loss of confidentiality (see below). To minimize the risk of loss of confidentiality, participants will be told that whatever they say in these group settings or report in the study surveys is confidential.

We will not be collecting any sensitive patient data, such as experiences with asthma death or asthma-related depression. However, we will be asking about previous asthma attacks that may have been life-threatening which may be a traumatic memory. Subjects will be allowed to skip any questions that they find troubling and should there be any indication of imminent medical or psychological risk associated with any aspect of the study, participants will be referred to previously identified resources in the study catchment areas. In concert with our partners, we will establish specific medical and counseling protocols prior to study onset. To that end we have established the following procedure: all study visits will take place at the FQHCs which have urgent medical and psychological services available on-site for evaluation and have set procedures for the timely and safe transfers of acute medical and psychological conditions to appropriate services.

To the best of our knowledge, the risks of obtaining spirometry (a measure of obstructive airflow) is minimal as this procedure is typically performed in community-based health screenings.

Study participants will be informed that they have a right to withdraw from the study at any stage.

